Primary objective: Determine biosignatures sensitive to pregnenolone

- Determine if an increase in amygdala-PCC functional connectivity ($d \ge 0.5$) is observed with pregnenolone, as compared to placebo in women with MDD.
- Determine if an increase in dIPFC-insula functional connectivity ($d \ge 0.5$) is observed with pregnenolone, as compared to placebo in women with MDD.
- Determine if an increase in occipital GABA concentration ($d \ge 0.5$) is observed with pregnenolone, as compared to placebo, in women with MDD.

Secondary objectives:

- Assess safety and tolerability of pregnenolone at the doses tested.
- Demonstrate increases in serum pregnenolone and allopregnanolone levels with pregnenolone administration (bioavailability).
- Identify a dose of pregnenolone that demonstrates bioavailability, tolerability and that is associated with a significant change in a biosignature.

Design and Outcomes

In this phase, 31adult women meeting criteria for Major Depressive Disorder (MDD) as defined in DSM 5, will be randomized to a double-blind, placebo-controlled, crossover phase I clinical trial of pregnenolone (i.e. each participant receives 500 mg/d, 800 mg/d pregnenolone and placebo in random order).

The study will consist of three 7-day treatment exposures to each pregnenolone dose and placebo (in random order) with a 14-day washout between each exposure. Baseline evaluation will include medical and psychiatric history, psychiatric interview, standard laboratory analyses (i.e., blood draw, ECG), and a brief cognitive battery. Neuroimaging will be collected after each study drug or placebo administration. Study drug tolerability and participant safety will be assessed throughout the study (6 in-clinic visits + a safety visit) using structured clinical interviews, self-report questionnaires, and standard laboratory analyses.

NCCIH R61 Study Diagram

Procedure	Baseline	Visit	Visit	Visit	Visit	Visit	Visit	Safety
Procedure	Daseillie	1	2	3	4	5	6	Visit
Consent	Х							
SCID-CV for DSM 5	Х							
HRSD	X	X	X	X	X	X	X	X
SAFTEE	Х		Х		X		X	X
C-SSRS	X		X		Х		X	Х

Time	~3 hr	~40 min	~2.5 hr	~40 min	~2.5 hr	~40 min	~2.5 hr	~1.5 hr
Pregnenolone administration		X		Х		X		
MRI scan			X		X		X	
Physician follow-up		X	X	Х	X	X	X	X
Screen								\ \ \ \ \ \ \ \ \ \ \ \ \ \ \ \ \ \ \
Urine Pregnancy Test & Drug	X							
ECG	X	-	X					^
Vital signs	X	X	X	X	X	X	X	X
Blood draw	X	\ \ \ \ \ \ \ \ \ \ \ \ \ \ \ \ \ \ \	X	V	X	V	X	X
Physical Exam	X						X	
Psychiatric Evaluation	X							
UCLA Loneliness Scale	X		Х		X		X	

Notes: SCID-CV – Structured Clinical Interview Clinician Version. HRSD – Hamilton Rating Scale for Depression. SAFTEE – Systematic Assessment for Treatment Emergent Events. C-SSRS – Columbia-Suicide Severity Rating Scale. ECG – Electrocardiogram. MRI – Magnetic Resonance Imaging.

Interventions and Duration

Pregnenolone, an over-the-counter supplement, is a naturally occurring neurosteroid made in the adrenal glands and brain. In the R61 phase, two different pregnenolone doses will be tested and compared to placebo in a double-blind, crossover design. Participants will be assigned to receive pregnenolone (500 mg/d, 800 mg/d) or placebo for 7 days beginning at Visit 1. The study will consist of three 7-day treatment exposures (in random order) to each pregnenolone dose and placebo with a 14-day washout between each exposure. The first 7-day treatment will begin at Visit 1, the second treatment at Visit 3, and the third treatment at Visit 5. An independent unblinded statistician (see Study Team Roster) not involved in data analysis will perform randomization to determine the order of treatment administration. The 14-day washout period between each treatment will serve to collect neurosteroid serum levels and neuroimaging biosignature.

Pregnenolone and capsules will be purchases from MEDISCA (Irving, TX) and supplied to the Abrams Royal Compounding Pharmacy (Dallas, TX). Abrams Royal Pharmacy is a PCAB accredited pharmacy and will prepare pregnenolone and placebo for encapsulation. The placebo will be identical in appearance to pregnenolone, and will be delivered by the pharmacy staff to the investigator's office.

Sample Size and Population

Twenty-six women (n=31) with MDD, who also meet additional eligibility criteria as outlined in Section 4, will be randomized into the study. A sample size of n= 31 would allow for > 25% attrition (much higher than expected) and still provide > 90% power with an α = 0.05 in the R61 phase of the experiment. A sample size of 31 is adequate to detect within-group dose and condition differences with an effect size (Cohen's d) of about 0.82 (medium to large).

1. STUDY OBJECTIVES

1.1 Primary Objectives (biosignature determination)

- Determine if an increase in amygdala-PCC functional connectivity $(d \ge 0.5)$ is observed with pregnenolone, as compared to placebo in women with MDD.
- Determine if an increase in dIPFC-insula functional connectivity ($d \ge 0.5$) is observed with pregnenolone, as compared to placebo in women with MDD.
- Determine if an increase in occipital GABA concentration ($d \ge 0.5$) is observed with pregnenolone, as compared to placebo, in women with MDD.

1.2 Secondary Objectives

- Assess safety and tolerability of pregnenolone at the doses tested.
- Assess bioavailability of pregnenolone by demonstrating increases in serum pregnenolone and allopregnanolone levels with pregnenolone administration.
- Identify a dose of pregnenolone that demonstrates bioavailability, tolerability and that is associated with a significant change in a biosignature.

2. BACKGROUND AND RATIONALE

2.1 Background on Condition, Disease, or Other Primary Study Focus

Pregnenolone, an over-the-counter supplement, is a naturally occurring neurosteroid made in the adrenal glands and brain. Preclinical research suggests pregnenolone has antidepressant, cognitive enhancing, and neuroprotective properties, particularly in women. Given the widespread availability of pregnenolone, as well as promising preclinical and clinical data, this trial proposes to further examine its use for depression. The proposed study will assess the ability of pregnenolone to engage a biosignature in people with major depressive disorder (MDD), as well as assess the safety and tolerability of pregnenolone. Additionally, this trial will provide needed information for further clinical research with this supplement that will be addressed in the R33 phase.

2.2 Study Rationale

Pregnenolone is an endogenous neurosteroid synthesized from cholesterol in the adrenal glands and brain. Pregnenolone serves as a precursor to downstream neurosteroids, including allopregnanolone, pregNANolone (we will use capital letters to distinguish it from pregnenolone), and dehydroepiandrosterone (DHEA). Although

pregnenolone is a readily available, over-the-counter (OTC) supplement, research on its use in humans is quite limited. Studies from the 1950's suggested pregnenolone was associated with improvement in irritability, insomnia, depression and anxiety (for a review, see Sells(1)). Recent studies suggest that pregnenolone may be useful for positive(2) and negative(3) symptoms of schizophrenia. In one of these studies, changes in the Brief Assessment of Cognition in Schizophrenia (BACS) correlated with increases in serum pregnenolone levels.(3)

Preclinical data suggest pregnenolone and other neurosteroids may be useful for MDD. Several lines of preclinical and clinical research suggest pregnenolone may be useful for mood and anxiety disorders. Chronic social isolation in rats is associated with anxiety and depression-like behaviors,(4) as well as reduction in cerebrocortical pregnenolone and allopregnanolone levels.(5) Administration of the pregnenolone metabolite, allopregnanolone, is associated with a reduction in anxiety behaviors in animal models.(6) A synthetic analogue of pregnenolone that specifically binds to microtubule associated protein 2 (MAP-2) receptor had potent antidepressant effects in the forced swim test,(7) as well as more persistent effects than fluoxetine in the isolation-rearing model that induces depression-related behaviors. Pregnenolone and its metabolites also have effects on microtubules, (8, 9) and other mechanisms relevant to depression including effects on N-methyl-D-aspartic acid (NMDA), gamma-amino butyric acid (GABA) and nicotinic receptors, acetylcholine, glycine, and voltage gated calcium and potassium channels.(10) Furthermore, major metabolites of pregnenolone are the GABAergic neurosteroids, allopregnanolone and pregNANolone.(11) Thus, pregnenolone and its metabolites act through mechanisms relevant to depression and anxiety. Because GABAergic neurosteroids are produced by pregnenolone, and low levels of brain GABA are reported in MDD,(12) brain GABA changes that are consistent with an antidepressant response as biosignatures will be explored in this proposal.

Human data also suggest pregnenolone may be useful for MDD: George et al. examined pregnenolone levels in the cerebrospinal fluid (CSF) of persons with mood disorders and healthy controls.(13) Patients with mood disorders had mean CSF pregnenolone levels 40% lower than controls. Lower pregnenolone levels appeared to be at least partially state dependent in that levels were 50% lower than controls in those currently depressed, but only 30% in those with a past mood disorder. Lower levels of serum pregnenolone were reported in anxiety disorders.(14)·(15) PI on the current application conducted two placebo-controlled pilot studies of pregnenolone in bipolar or unipolar depressive disorders. Both studies had positive findings (section 3.3.).(16) In the first study, 70 outpatients with unipolar (MDD) or bipolar depression were given pregnenolone (100 mg/d) or placebo for eight weeks. The pregnenolone group showed greater improvement in depressive symptoms than placebo group (section 3.3.a.). In the second study, 80 outpatients with bipolar depression were given pregnenolone (500 mg/d) or placebo for 12 weeks. The pregnenolone-treated group showed significant improvement in depressive symptoms as compared to placebo (section 3.3.b.). The

higher dose (500 mg) was associated with a larger effect size for depression improvement. In both studies, women demonstrated a more favorable response to pregnenolone, relative to placebo, than men. In addition, in the second study, women showed improvement in cognition with pregnenolone, and changes in serum pregnenolone and other neurosteroid levels showed very strong correlations with improvement in depressive and anxiety symptoms. Sripada et al. reported a single 400 mg pregnenolone dose by mouth was associated with an increased activity in the dorsal medial prefrontal cortex (dmPFC) relative to placebo, as well as changes in resting state functional connectivity (rsFC) between the amygdala and dmPFC, precuneus and hippocampus, as well as large increases in serum neurosteroid levels.(17, 18) We also collected rsFC data on pregnenolone and observed changes in connectivity consistent with an antidepressant effect in several brain regions (section 3.3.d.). Therefore, rsFC changes as biosignatures will be tested in this proposal.

Pregnenolone and downstream neurosteroids synthesized from it 1) act on neurotransmitters relevant to depression and anxiety, 2) demonstrate antidepressant and anxiolytic properties in animals, 3) have cognitive-enhancing properties that could be particularly useful in MDD, 4) show, based on our pilot data, promise in treating depression, particularly in women. Given the data above, we propose to develop pregnenolone as an MDD treatment in women. As such, pregnenolone would be the first antidepressant to demonstrate sex differences in treatment response. Findings from the study may increase industry interest in development of neurosteroid analogues for brain diseases in the same way that ketamine research has increased research and development in NMDA-receptor antagonists for depression.

Pregnenolone has a favorable safety and tolerability profile. The reported side effects in clinical trials using the 500 mg/day pregnenolone dose were primarily mild restlessness, mild muscle pain or stiffness, and mild coldness in the extremities (3). It is also theoretically possible that pregnenolone (due to its neurosteroid properties) could interact with oral contraceptive agents, thus women taking oral contraceptive medications containing progestin will be excluded from the study (or discontinued from the study if they initiate treatment with oral contraceptives post randomization). It is possible that other unforeseen risks of pregnenolone may exist. All participants will be carefully monitored at each study visit to ensure safety and to minimize any risks that may arise due to pregnenolone. Please refer to Section 7 for a full summary of potential risks.

3. STUDY DESIGN

In the R61 phase, 31 adult women with mild to moderate MDD (based on DSM-5 criteria) meeting inclusion and exclusion criteria will be enrolled in a double-blind, placebo-controlled, crossover phase I clinical trial of pregnenolone (i.e., each participant receives 500 mg/d, 800 mg/d pregnenolone and placebo in random order).

During Visit 1, participants will be started on either 500 mg of pregnenolone, 800mg of pregnenolone, or placebo (order randomized by a study statistician with no participant contact). Participants will continue taking study medication for 7 days before undergoing a 14-day washout period. The second treatment exposure will begin at Visit 3, and the third and final treatment at Visit 5. All visits will have a visit window (see Section 6.2.4) to accommodate participant schedule and MRI scanner schedule. The medication-free washout period will serve to collect neurosteroid serum levels and neuroimaging biosignature. Throughout the study, three total treatment exposures (7 days on/14-day washout) will take place (two pregnenolone doses and placebo).

The following endpoints will be evaluated in the R61 Phase of the trial:

Primary endpoints (biosignature determination):

- Determine if an increase in amygdala-PCC functional connectivity ($d \ge 0.5$) is observed with pregnenolone, as compared to placebo in women with MDD.
- Determine if an increase in dIPFC-insula functional connectivity ($d \ge 0.5$) is observed with pregnenolone, as compared to placebo in women with MDD.
- Determine if an increase in occipital GABA concentration ($d \ge 0.5$) is observed with pregnenolone, as compared to placebo, in women with MDD.

Secondary endpoints:

- Assess safety and tolerability of pregnenolone at the doses tested.
- Assess bioavailability of pregnenolone by demonstrating increases in serum pregnenolone and allopregnanolone levels with pregnenolone administration.
- Identify a dose of pregnenolone that demonstrates bioavailability, tolerability and that is associated with a significant change in a biosignature.

All study procedures, with exception of neuroimaging will take place at the offices of the Psychoneuroendocrine (PNE) Research Program (BL8.224) in the Department of Psychiatry at UT Southwestern Medical Center, Dallas, TX over approximately a 2-year period. All neuroimaging procedures will take place at the Advanced Imaging Research Center (AIRC) at UT Southwestern, and will be performed by a licensed MRI technologist.

The approximate duration of study participation for an individual participant will be 9 weeks with additional 2 weeks reserved for unforeseen scheduling events. All participants will be given pregnenolone (2 x 250 mg or 2 x 400 mg capsules) and placebo at some point during the study (depending on the order of randomization). Oral encapsulated pregnenolone and placebo will be prepared by the Abrams Royal Compounding Pharmacy and distributed to the investigator by the pharmacy staff. The laboratory of [name] at Duke University will perform the neurosteroid assays.

4. SELECTION AND ENROLLMENT OF PARTICIPANTS

4.1 Inclusion Criteria R61

Potential participants must meet **ALL** of the inclusion criteria listed below to participate in this study. Following baseline visit, participants may be discontinued from

the study if they meet any of the criteria outlined in Section 8. Inclusion criteria are as follows:

- Women, ages 18-65 years, with current MDD (mild or moderate severity per DSM-5) based on SCID-CV.
- No psychotropic medications, other than PRN (as needed) hypnotics, within 28 days of randomization (medication free).
- PRN hypnotics allowed up to 3 days prior to study drug administrations but not while receiving study drug.
- Ability to understand study procedures and to comply with them for the entire length of the study.

4.2 Exclusion Criteria R61

Participants who meet **ANY** of the following exclusion criteria at baseline will not be eligible for participation in the study. Following baseline visit, participants may be discontinued from the study if they meet any of the criteria outlined in Section 8. Exclusion criteria are as follows:

- Severe MDD based on DSM-5 severity criteria and/or a baseline HRSD score > 27 (consistent with severe depressive symptom severity).
- High risk for suicide (active SI with plan/intent or > 2 lifetime attempts in lifetime or any in the past 6 months).
- Treatment resistant depression (fail two adequate antidepressant trials or ECT during current episode).
- Vulnerable populations (e.g. pregnant/nursing, severe cognitive or intellectual impairment, incarcerated).
- Coronary artery disease, atrial fibrillation, stroke, deep vein thrombosis, pulmonary embolism or blood clotting disorder, or any severe, life threatening or unstable, medical condition.
- History of allergic reaction or side effects with prior pregnenolone use.
- Current substance use disorder defined as meeting criteria for a use disorder based on the SCID interview and self-reported use within the past 3 months, or a positive baseline urine drug screen.
- Current psychotic features (hallucinations, delusions, disorganized thought processes) or eating disorders.
- Anxiety disorders of sufficient severity to be the primary focus of clinical attention (e.g. severe obsessive compulsive or post-traumatic stress disorders).
- Currently undergoing evidence-based cognitive behavioral therapy (CBT) treatment for depression.
- Hormone-sensitive conditions (i.e. breast cancer; uterine/ovarian cancer, endometriosis, uterine fibroids).
- Clinically significant laboratory, physical examination, or electrocardiogram (ECG) findings, including vital signs of diastolic blood pressure > 100, systolic blood pressure > 150, heart rate > 100 or < 50, temperature > 100.5 degrees F (38 degrees C).

Currently using oral contraceptives containing progestin (barrier methods allowed)

4.3 Study Enrollment Procedures

Participants will be recruited through various forms of advertising available to the UT Southwestern researchers, specifically 1) paid and free advertising and 2) patients treated at UT Southwestern. IRB-approved flyers will be posted at various clinics affiliated with UT Southwestern, as well at the local mental health clinics (e.g., Dallas Metrocare Clinics), women's health centers, and community clinics. A weekly announcement regarding the study will be posted in "Campus Updates" – a free UT Southwestern weekly news service. Paid advertising may include newspaper and radio ads that the group has used in the past. Other free internet advertising sources may be utilized as needed.

UT Southwestern also has access to a Volunteer Research Participant Registry operated through the Clinical Trial Infrastructure at UT Southwestern. Registry volunteers are UT Southwestern patients who have agreed to be contacted with research opportunities. The registry will be used in the study. Additionally, the study will also be advertised to participants who have previously participated in other research studies and agreed to be contacted for future studies.

Physician referrals will be obtained using medical record review from under the IRB-approved HIPAA waiver. UT Southwestern has a large private practice Psychiatry clinic, as well as numerous other outpatient clinics, from which the physician referrals will be obtained.

Once participants have been identified, a brief phone interview will be held to see if the participant may be eligible for the study. The phone interview will include eligibility questions about the participants (e.g., age, psychiatric and medical history, concomitant medications, etc.). Participants who are determined "ineligible" via phone interview (preconsent) will be noted on the "Screening Log" as ineligible and no further contact will be made.

If the participant seems eligible for the study, they will be scheduled for a Baseline visit, at which time a written informed consent will be obtained. In order to be eligible for the study, participants will be required to consent for themselves, thus a legal authorized representative will not be needed. Only IRB-approved study personnel will be eligible to consent participants under the direction of the PI.

Participants meeting the required inclusion criteria and none of the exclusion criteria, as determined by the PI or study clinician, will be randomized into the study. Any participants who sign a consent will be noted in the "Enrollment Log". If a participant is determined to be ineligible for the study post-consent, they will be considered a "screen fail" and an appropriate note will be made in the log.

Randomization will be performed by a statistician using a random number sequence (SAS Proc Plan). A randomization list will be maintained in a password protected folder by an unblinded staff member with no participant contact. In the R61 phase, a crossover design will be used so each participant will receive each of three study drug conditions in a random order. All tests will be 2-sided with p< 0.05 to assess significance.

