9. STATISTICAL CONSIDERATIONS

9.1 General Design Issues

The R61 phase involves a randomized, double-blind, cross-over design of 500 mg/d pregnenolone, 800 mg/d pregnenolone, and placebo for seven days with a 14-day washout between each exposure in 31 women with MDD.

Hypothesis: Pregnenolone is associated with improvement in depressive symptom severity in women that is associated with changes in rsFC and GABA.

Primary Study Aims R61 Phase (biosignature determination):

- Determine if an increase in amygdala-PCC functional connectivity ($d \ge 0.5$) is observed with pregnenolone, as compared to placebo in women with MDD.
- Determine if an increase in dIPFC-insula functional connectivity ($d \ge 0.5$) is observed with pregnenolone, as compared to placebo in women with MDD.
- Determine if an increase in occipital GABA concentration ($d \ge 0.5$) is observed with pregnenolone, as compared to placebo, in women with MDD.

Secondary Study Aims R61 Phase:

- Assess safety and tolerability of pregnenolone at the doses tested.
- Assess bioavailability of pregnenolone by demonstrating increases in serum pregnenolone and allopregnanolone levels with pregnenolone administration.

• Identify a dose of pregnenolone that demonstrates bioavailability, tolerability and that is associated with a significant change in a biosignature.

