9.2 Sample Size and Randomization

Data from pooled randomized, controlled trials of how standard depression therapies influence proposed neuroimaging biosignatures (GABA) in a depressed population, and our rsFC connectivity data with pregnenolone, suggest that a sample size of n=31 would allow for > 25% attrition (higher than expected), and provide > 90% power with an α = 0.05 in the R61 phase of the experiment.(22) A sample size of 31 is adequate to detect within-group dose condition differences (500 mg vs. 800 mg vs. placebo) with an effect size (Cohen's d) of about 0.82 (medium to large) in the first phase. Thus, each pregnenolone dose will be compared to placebo separately. The reported d for changes in occipital GABA with depression treatment ranges from 1.28 to 1.59. The rsFC increase with pregnenolone, as compared to placebo, between the amygdala (seed region) and PCC in our pilot had an effect size of d = 3.28.

Randomization will be performed by an independent unblinded statistician (see Study Team Roster) not involved in data analysis prior to recruitment using a random number sequence (Statistical Analysis System [SAS] Proc Plan). A randomization list will be maintained in a password protected folder by an unblinded staff member with no participant contact. See section 6.2.3 Blinding for more information regarding the unblinding procedures.

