9.6 Data Analyses

Primary Aims:

To determine biosignature(s) sensitive to pregnenolone, scores on biosignatures will be compared between conditions using a random regression model with time and dose (500mg, 800mg, placebo) as within-subject factors using the PROC MIXED function. In determining statistical significance, Bonferroni corrections will be made to control for Type I error rates. Additionally, to explore the role neurosteroid levels have in the relationship between dose condition and biosignatures, separate mediational path models will be run. Specifically, following Preacher and Hayes' (2008)(26) bootstrap procedure, 5,000 bootstrap resamples will be examined using the Process macro (Hayes, 2013)(27) for SAS 9.4. In the path model, each biosignature will be regressed separately on to dose condition with neurosteroid levels included as a mediator (indirect effect). The following covariates will be included in this exploratory model: baseline scores on HRSD, age, depression severity, and depression duration.

95% confidence intervals will be examined and if the confidence interval does not contain zero, the effect will be considered statistically significant.

Secondary Aims: Tolerability

Tolerability will be defined as no SAEs related to the study medication and no more than 10% of participants have a moderate or severe AE that is related to the product. For dichotomous outcomes (e.g. drop out vs. completer) PROC NLMIXED will be used where dose and time will be added as within-subject factors and status as a dichotomous outcome variable.

Secondary Aims: Bioavailability

To assess **bioavailability** of pregnenolone and allopregnanolone, mean pregnenolone and allopregnanolone levels in each condition will be compared using a one-way repeated measures ANOVA. PROC ANOVA will be used to examine overall differences for each outcome, Bonferroni corrections will be made to control for Type I error rates, and Tukey's post hoc procedure will be used to examine pairwise comparisons for each condition.

Secondary Aims: Pregnenolone Dose

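### The plan does not require the six treatment orders to be balanced, and two secondary analyses (possibly also the go/no-go effect size) carry no period term: a modest loss that costs almost nothing to avoid

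*Combined protocol and SAP*

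**What the plan says.** The trial is a three-condition, three-period "cross-over design of 500 mg/d pregnenolone, 800 mg/d pregnenolone, and placebo for seven days with a 14-day washout between each exposure in 31 women". Section 4.3 states that "each participant will receive each of three study drug conditions in a random order". Three conditions in three periods give six possible orders.

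Two places describe how the list is made. Section 4.3 says "Randomization will be performed by a statistician using a random number sequence (SAS Proc Plan"). Section 9.2 assigns the task to an independent statistician "not involved in data analysis prior to recruitment using a random number sequence (Statistical Analysis System [SAS] Proc Plan"). Section 5.1 only refers back to 9.2, and section 6.2.3 adds only that the list exists before recruitment. None of them mentions blocks, a Latin or Williams square, or equal use of the six orders.

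Section 9.6 treats period differently from one analysis to the next:

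- **Primary biosignature model:** time and dose as within-subject factors. There is one scan per treatment course, so time acts as the period term.
- **Dichotomous tolerability outcomes:** dose and time.
- **Bioavailability:** mean serum levels "in each condition will be compared using a one-way repeated measures ANOVA", with no period term.
- **Dose selection:** a one-way repeated-measures MANOVA with dose only.
- **Go/no-go rule:** Cohen's d of at least 0.5 on two of three biosignatures, without saying whether d comes from the time-adjusted model or from raw condition means.

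**The concern.** In a small crossover, using the six orders equally makes treatment orthogonal to period. Without that balance, one of two things happens, depending on the analysis.

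- **Period is fitted.** Dose is partly collinear with period and the contrast loses precision. No bias arises.
- **Period is not fitted.** Any drift over the three periods that is common to all women enters the dose-placebo difference, by an amount set by how unevenly the conditions happen to fall.

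The second matters most for the go/no-go d, because it is compared with a fixed threshold and section 9.3 confirms that there is no baseline scan to absorb drift.

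**Working it through.** **Inputs.** N = 31 (section 9.1); more than 25% attrition, power above 90% and α = 0.05 (section 9.2); two-sided tests (section 4.3); d about 0.82 (section 9.2). The plan does not say what d is standardised by; I read it as mean difference over SD of differences. The list is assumed simple random, each order having probability 1/6. The plan does not state this.

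**The plan's own figure.** Section 9.2 says that 31 women "would allow for > 25% attrition (higher than expected), and provide > 90% power with an α = 0.05". 31 × 0.75 = 23.25, so about 23 completers. A paired t-test with d = 0.82 and two-sided α = 0.05 has 96.4% power at n = 23 and 99.3% at n = 31. On this reading the claim of more than 90% is met.

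**Precision when period is fitted.** Let T be the 3 × 3 table of period-by-condition counts. With complete data, the information for treatment after removing woman and period is N·I − T′T/N, with I the identity matrix. With perfect balance the variance of a dose-placebo contrast is 2σ²/N. Ratios to that value over 20,000 simple random lists:

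| N | mean | median | 95th percentile |
|---|---|---|---|
| 31 | 1.035 | 1.023 | 1.107 |
| 23 | 1.049 | 1.032 | 1.15 |

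A balanced list of 31 (order counts 6, 5, 5, 5, 5, 5) gives 1.001, with every condition 10 or 11 times in every period. Under simple random lists a condition expected 31/3 = 10.3 times in a period falls between 5 and 16 times in 95% of lists.

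**Effect on power** (divide d by the square root of the ratio):

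| d | N | balanced | average list | 95th-percentile list |
|---|---|---|---|---|
| 0.5 | 31 | 76.8% | 75.4% | 72.5% |
| 0.5 | 23 | 63.0% | 60.9% | 57.1% |
| 0.82 | 23 | 96.4% | 95.6% | 93.9% |

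The ratios used are 1.035 and 1.11 at N = 31, and 1.05 and 1.15 at N = 23.

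**Shift when period is not fitted.** Over the six orders, the difference in position between a dose and placebo is ±1 in four and ±2 in two. Its mean square is (4 × 1 + 2 × 4)/6 = 2. The mean position difference in a simple random list therefore has SD √(2/31) = 0.25 period; simulation gives a 95th percentile of 0.48. At N = 23 the values are √(2/23) = 0.29 and 0.57.

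With a linear drift of g SD per period, the shift is g times that difference. The documents give no g, so 0.1 to 0.3 is an assumption. At N = 31:

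- typical list: 0.25 × 0.1 = 0.03 to 0.25 × 0.3 = 0.08 SD
- 95th-percentile list: 0.48 × 0.1 = 0.05 to 0.48 × 0.3 = 0.15 SD

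The largest of these is 0.15/0.5 = 30% of the go threshold.

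**What blocks leave after dropout.** With 31 women in blocks of six and 8 lost at random, the mean variance loss among the 23 completers is about 1.3%, against about 5% for simple random lists. The position SD is √(2/23 × 8/30) = 0.15 (0.16 by simulation, which includes the one odd order), against 0.29. Blocks about halve the position imbalance; they do not remove it.

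**The case against.** The strongest reply is that the documents are silent about restriction. A reader might infer that the orders are drawn without restriction, but neither section says so. PROC PLAN can produce a blocked list as easily as a simple random one, and an independent statistician may already have used blocks. That stands: what can be shown is an unspecified property of the list, and every figure above is conditional on its being simple random. The gap still matters, because a simple random list would comply fully with the text.

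A reader might also infer that the primary result is exposed to period drift. It is not: the primary model and the dichotomous tolerability model include time. Only the bioavailability ANOVA, the dose-selection MANOVA and, if taken from raw means, the go/no-go d are exposed. For serum levels, drift from scanner habituation or mood change is hard to argue, so the ANOVA is the least worrying of the three.

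Third, a larger precision cost can be quoted by taking the less precise of the two dose-placebo contrasts in each list: 5% on average and 13% at the 95th percentile with 31 women. That describes the worse of two contrasts, so it is not the expected cost for a given comparison.

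Finally, the precision loss is small beside the margin in section 9.2, and dropout disturbs even a blocked list. Both are true. They limit the size of the point and are a reason to fit period as well as to block.

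**Conclusion.** The point holds as a modest improvement at almost no cost. Sections 4.3 and 9.2 require no balance over orders or periods. If the list is simple random, a given period-adjusted contrast loses about 3.5% in variance on average at N = 31 (11% at the 95th percentile) and about 5% (15%) at N = 23, or about 1 to 2 points of power on average. In the analyses without period, the shift is about 0.03 to 0.08 SD typically and 0.05 to 0.15 SD in a bad list, for an assumed drift of 0.1 to 0.3 SD per period. If there is no drift, there is no shift.

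The documents do not support a claim that the list is in fact unbalanced, or that the primary biosignature tests are biased. Nor does any of this invalidate the trial.

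**What to change.** 1. In sections 4.3 and 9.2, state that the PROC PLAN list uses permuted blocks of six, each containing all six orders of the three conditions once. Thirty-one women use five full blocks plus one order of a sixth (5 × 6 + 1 = 31). If recruitment has begun, apply this to the unallocated numbers. If the existing list is already balanced, say so; nothing else about the list need change.
2. In section 9.6, add period to the bioavailability and dose-selection models.
3. In section 9.6, state that the go/no-go Cohen's d is taken from the period-adjusted contrast, and name its standardiser.

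Items 2 and 3 are needed even with blocks, because dropout leaves some imbalance. The cost is regenerating the list at most, plus a few sentences. No extra women, visits or measurements are needed.
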